12.0 STUDY MONITORING

12.1 Adverse Event Reporting Guidelines

12.1.1 Reporting Procedures

Serious adverse Events (SAE's) that are unexpected and/or definitely, probably or possibly related to protocol therapy should be reported to:

The data manager will complete the CTO SAE Report form. The Clinical Trials Office (CTO) staff will coordinate the reporting process between the Investigator and the IRBMED as well as any other applicable reporting. Copies of all related correspondence and reporting documents will be maintained in the subject research chart and/or regulatory file as appropriate.

Adverse event (AE) monitoring and reporting is a routine part of every clinical trial. Data on adverse events will be collected from the time of the initial intervention through 30 days following the completion of radiation therapy. Serious Adverse Events (SAEs) will continue to be followed until resolution or clearly determined to be due to a patient's stable or chronic condition or intercurrent illness(es).

The investigator is responsible for the detection, documentation, grading and assignment of attribution of events meeting the criteria and definition of an AE or SAE. The definitions of AEs and SAEs are given below. It is the responsibility of the principal

investigator to ensure that all staff involved in the trial are familiar with the content of this section.

Any medical condition or laboratory abnormality with an onset date before initial investigation agent/intervention administration is considered to be pre-existing in nature. Any known pre-existing conditions that are ongoing at time of study entry should be considered medical history and recorded in the appropriate section of the case report form.

All adverse events occurring from the initial investigational agent/intervention administration through 30 days following the last dose of the investigational agent/intervention (end of RT) must be recorded as an adverse event in the patient's source documents and on the CRF regardless of frequency, severity (grade) or assessed relationship to the investigational agent/intervention.

In addition to new events, any increase in the frequency or severity (i.e., toxicity grade) of a pre-existing condition that occurs after the patient begins taking the investigational agent/intervention is also considered an adverse event.

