6.4 Radiation Toxicity

Toxicities will be assessed using diagnostic imaging and physical exam and neurologic testing including MMSE. Toxicities will be graded clinically according to Common Toxicity Criteria (CTC).

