10.0 PATIENT ASSESSMENTS

10.1 Study Plan

- 10.1.1 Patients will receive concomitant temozolomide (75 mg/m² daily for 6 weeks) with radiotherapy as per standard of care.
- 10.1.2 Temozolomide will be taken orally prior to RT. The physician will discuss with the patient any eating restrictions, when other medications should be taken, and when temozolomide should be taken on the days without RT as per standard of care.
- 10.1.3 Adjuvant temozolomide 150-200 mg/m² D1-5 q28 days (+/- 5 days) for six cycles will be started approximately 4 weeks following completion of radiotherapy. Additional cycles may be continued at investigator's

- discretion. The first cycle will be prescribed at 150 mg/m², then increase to 200 mg/m² at cycle 2, toxicity permitting, as per standard of care.
- 10.1.4 Patients will receive RT at the University of Michigan or one of its affiliate centers. The patient will be considered eligible to receive concurrent and adjuvant chemotherapy through outside physicians closer to his/her home with continued follow-up at the University of Michigan per study guidelines

10.2 Study Specific Calendar	Pre-Ry		Prior to Each Chemotherapy Cycle	Follow-up Evaluation ^{a,g}					
			-			Mon	th		
				1	3	5	7	13	19
History & Physical Exam	X			Х	Х	X	X	X	Χ
KPS & Neurological Exam	х	x ^b (wk 6 of RT		x	х	x	X	X	X
QOL Evaluation/MDASI/MMSE ^c	х	x ^c (wk 6 of RT)		x	х	х	Х	X	Х
CBC w/ Diff, Platelets	Х	Xq	$\mathbf{X}_{\mathbf{q}}$						
Comprehensive metabolic panel	x		\mathbf{x}^{d}						
Neurocognitive evaluation	x b			x			Х		X
Gadolinium enhanced Brain MR ^e	Х			Х	Х	Х	х	Х	х
Advanced MRI	х	X ^f (wk 4 of RT)			x ^f				
11C MET PET	X ⁱ (optional)	X ^f (wk 4 of RT)							
Toxicity Notation	х	Х		Х	х	X	X	X	Х

- a) Timing of follow ups (1 month = 28 days): As per standard of care, patients will typically be seen in follow-up 1 month after completion of chemoradiation, then every 2 months +/- 2 week window. At the physician's discretion, after the first 6 months, follow-up visits may be approximately every 3 months. If a patient's temozolomide cycles are prolonged due to time for blood count recovery or other factors, assessments may be delayed in accord with the temozolomide cycles. At follow-up visits, history and physical exam, KPS and neurologic exam, and toxicity evaluations will be undertaken.
- b) KPS and recording of steroid and anticonvulsant dose will be required during week 6 of radiotherapy. NANO evaluation will be required at baseline

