Patients will complete neurologic exam, mini mental status exam and EORTC global QOL questionnaire and specific brain module and MDASI-BT before, during and after treatment. The results will be summarized descriptively over time as well as by radiation dose. The relation between these outcomes and survival will be assessed by using QOL numbers as (possibly time dependent) predictors in a Cox regression model. Every effort will be made to avoid missing data. Missing data will be carefully considered as to whether it is missing at random or not. Mixed models with subject level random effects can provide valid estimation and inference under certain patterns of informative missingness and will be utilized where warranted. We will also perform simple checks whether for example subjects with decreased QOL are more likely to drop out. For example, we will compare observed QOL at time t amongst patients who did or did not drop out (i.e. decline to provide QOL data) by time t+1.

11.7 Interim analysis:

Due to a possible increased incidence of grade 3 or higher CNS toxicity (possibly, probably, or definitely related to treatment), we will analyze the data 6 months after the 20th patient completes radiation. At this point approximately 29 patients, out of the planned total of 40 patients eligible for radiation boost, will have been enrolled on the trial. It is possible that 6 patients will experience toxicity prior to this time point, in which case, the trial would be halted as soon as the 6th patient experiences toxicity. If the number of patients, out of the first 20, with toxicity (as defined above) is 6 or greater, the trial will be stopped due to possible safety concerns. The operating characteristics of this stopping rule are given in Table 1 below. When the true toxicity rate is 10%, just

1% of trials will stop early. On the other hand, if the probability of toxicity is 40%, 87% of trials will stop early. We note here that we do not expect to see excessive toxicity in this study because the volume of brain treated with the experimental (boost) dose of radiation will be limited to 1/3 the volume of brain, shown to be safe based on our prior dose-escalation study based on standard MRI alone.³⁰

Table 1. The proportion of trials stopping

True P(tox)	10%	20%	30%	40%
Proportion of	1%	20%	58%	87%
Trials				
Stopping				
Early				

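### Adverse event collection ends 30 days after radiotherapy, but the section 11.7 stopping rule counts CNS toxicity for at least 6 months, and no section names the records it uses

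*Combined protocol and SAP*

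**What the plan says.** **Collection window.** Section 12.1.1 sets the limit twice. "Data on adverse events will be collected from the time of the initial intervention through 30 days following the completion of radiation therapy", and events "through 30 days following the last dose of the investigational agent/intervention (end of RT) must be recorded as an adverse event" in the source documents and on the CRF, whatever their grade or relationship to treatment.

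**Stopping rule.** Section 11.7 concerns grade 3 or higher CNS toxicity possibly, probably or definitely related to treatment. It says "we will analyze the data 6 months after the 20th patient completes radiation" and stops the trial if 6 or more of the first 20 patients are affected. It also provides for an earlier halt: "It is possible that 6 patients will experience toxicity prior to this time point", in which case the trial halts at the sixth patient.

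**Later assessment.** The calendar in section 10.2 has a toxicity row at follow-up months 1, 3, 5, 7, 13 and 19. Its footnote a adds: "At follow-up visits, history and physical exam, KPS and neurologic exam, and toxicity evaluations will be undertaken". Section 6.4 calls for CTC grading and goes on to describe acute, early delayed and late delayed effects.

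**Serious events.** Section 12.1.1 has serious events reported if they are ones "that are unexpected and/or definitely, probably or possibly related to protocol therapy should be reported to" the Clinical Trials Office process. It gives no explicit end date for this.

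**The concern.** The rule needs graded, attributed CNS events for months after radiotherapy. The section governing adverse event data closes collection at day 30. A data manager following 12.1.1 literally would stop entering events just before the period in which section 6.4.2 places early delayed neurological worsening (1-3 months after radiotherapy). Section 6.4.3 also lists radiation necrosis as a late effect, without an onset time.

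This is the only numerical safety rule for the 75 Gy boost. An undercount works in one direction only: it makes the trial less likely to stop when toxicity is high. Because the threshold is 6 of 20, a single uncounted patient can decide the outcome.

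**Working it through.** **1. Reproduce Table 1.** Inputs from 11.7: n = 20, stop at 6 or more, true toxicity rate p = 10, 20, 30, 40%. The formula is P(stop) = P(X ≥ 6), with X ~ Binomial(20, p). The results are 1.1, 19.6, 58.4 and 87.4%, against the stated 1, 20, 58 and 87%. The table is right, and it presumes that every qualifying patient is counted.

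**2. Effect of an undercount.** If k qualifying patients go unrecorded, stopping requires 6 + k true cases, so P(stop) = P(X ≥ 6 + k). This needs no assumption about onset times; it is conditional on k patients being missed.

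| True rate | 10% | 20% | 30% | 40% |
|---|---|---|---|---|
| All counted, X ≥ 6 | 1.1% | 19.6% | 58.4% | 87.4% |
| One missed, X ≥ 7 | 0.2% | 8.7% | 39.2% | 75.0% |
| Two missed, X ≥ 8 | 0.0% | 3.2% | 22.8% | 58.4% |

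The loss from one missed patient is P(X = 6): 0.9, 10.9, 19.2 and 12.4 percentage points.

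**3. Proportional undercount (illustration only).** The documents do not say what share s of qualifying events would be recorded, so s is assumed. P(stop) = P(X ≥ 6) with X ~ Binomial(20, p × s).

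| Assumed s | 10% | 20% | 30% | 40% |
|---|---|---|---|---|
| 0.90 | 0.7% | 13.6% | 46.4% | 78.3% |
| 0.75 | 0.3% | 6.7% | 28.4% | 58.4% |
| 0.50 | 0.03% | 1.1% | 6.7% | 19.6% |

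**4. Calendar coverage.** Footnote a to 10.2 defines a follow-up month as 28 days. On that scale the analysis falls at 6 × 28 = 168 days after the 20th patient's radiotherapy. The 12.1.1 window covers 30/168 = 18% of that patient's post-radiotherapy time, or (42 + 30)/(42 + 168) = 72/210 = 34% counted from the start of the 6-week course. Patients who finished earlier have longer follow-up, so the share is smaller for them. These are shares of time, not of events. Of the three toxicity visits due before the analysis (days 28, 84 and 140), only the first lies inside the window.

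**5. Can other provisions fill the gap?**

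- *Section 6.4:* grading by CTC, but no CRF entry, attribution or stated period.
- *Section 10.2, calendar and footnote a:* toxicity evaluated through month 19, with no statement that grade and attribution go on the CRF.
- *Section 12.1.1, investigator's duty:* "The investigator is responsible for the detection, documentation, grading and assignment of attribution of events meeting the criteria" for an AE or SAE. This does not extend the collection window set beside it.
- *Section 7.1, adjuvant temozolomide:* CRF entry only of the reasons for a dose reduction or delay.
- *Section 12.1.1, SAE reporting:* no explicit day-30 limit, but serious events only. Section 12.1.3.2 excludes hospitalization for expected cancer morbidity. Section 8.2 says admission for biopsy or resection of changes that could be progression or treatment effect may not count as an SAE.
- *Section 12.1.3.1:* the 7-day reporting of grade 3 events applies to unexpected ones, whereas 6.4.3 lists radiation necrosis as a possible effect.
- *Section 12.2:* quarterly committee meetings, but the safety item is described by reference to SAE/UaP reporting.

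None of these requires a non-serious related grade 3 or higher CNS event with onset after day 30 to reach the CRF with its grade and attribution.

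**The case against.** The best defence is that later toxicity is plainly meant to be assessed. Section 6.4 introduces subsections on early and late delayed effects, so its grading instruction reaches past day 30. The calendar schedules toxicity evaluation to month 19. Section 11.7 defines its event by grade, site and attribution, which implies that these are determined up to the analysis, and a specific rule would normally prevail over general reporting text. The seriousness criteria in 12.1.2 include significant incapacity and important medical events, so many grade 3 CNS toxicities would also be reported as SAEs. The CRFs and the institutional monitoring plan are not in these documents. Section 1.0 reports no necrosis or late CNS toxicity at or below 75 Gy in the earlier dose-escalation study.

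Much of this stands. It is wrong to say that toxicity goes unobserved after day 30, and the exposed group is limited to patients whose only qualifying event is non-serious and arises after day 30. The undercount figures are also conditional: they show what a miss would cost, not how likely one is.

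It does not remove the conflict. Section 12.1.1 says outright that collection and CRF recording end at day 30, while 11.7 depends on later events. Nothing states that the follow-up toxicity notes override that limit or feed the count.

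**Conclusion.** The concern holds. Sections 12.1.1 and 11.7 set incompatible periods, and no section names the records behind the stopping rule. No figure in the plan is wrong; Table 1 stands if capture is complete.

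At a true rate of 30%, one missed patient lowers the chance of stopping from 58% to 39%, and two lower it to 23%. At 40% the figures are 87%, 75% and 58%. How many would be missed cannot be estimated, because the documents give no onset distribution.

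The conclusion rests on reading 11.7 as counting all qualifying events among the first 20 patients up to the analysis. Counting each patient only to 6 months would still extend well past day 30. I am confident about the textual conflict; the size of any actual loss is unknown. It should be corrected, because the rule protects patients and should not depend on staff departing from 12.1.1.

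**What to change.** Reconcile 12.1.1 with 10.2 and 11.7:

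- **In 12.1.1,** state that the 30-day limit applies to general adverse events. Related grade 3 or higher CNS toxicity, serious or not, is to be graded, attributed and entered on the CRF at the toxicity visits already in 10.2, through at least the 11.7 analysis.
- **In 11.7,** state that the count is taken from these CRF entries together with reports of related SAEs.

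The cost is one sentence in each section and a few additional CRF entries. No visit is added, Table 1 does not change, and no treatment rule is affected.

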12.1.2 Definitions

Adverse event

Adverse event means any untoward medical occurrence associated with the use of a drug in humans, whether or not considered drug related.

An adverse event (also referred to as an adverse experience) can be any unfavorable and unintended sign (e.g., an abnormal laboratory finding), symptom, or disease temporally associated with the use of a drug, without any judgment about causality. An adverse event can arise from any use of the drug (e.g., off-label use, use in combination with another drug) and from any route of administration, formulation, or dose, including an overdose.

Adverse reaction

An adverse reaction means any adverse event caused by a drug. Adverse reactions are a subset of all suspected adverse reactions for which there is reason to conclude that the drug caused the event.

Suspected adverse reaction

Suspected adverse reaction means any adverse event for which there is a reasonable possibility that the drug caused the adverse event. For the purposes of IND safety reporting, 'reasonable possibility' means there is evidence to suggest a causal relationship between the drug and the adverse event. A suspected adverse reaction implies a lesser degree of certainty about causality than adverse reaction, which means any adverse event caused by a drug.

Unexpected

An adverse event or suspected adverse reaction is considered "unexpected" if it is not listed in the investigator brochure or is not listed at the specificity or severity that has been observed; or, if an investigator brochure is not required or available, is not consistent with the risk information described in the general investigational plan or elsewhere in the current application. "Unexpected," as used in this definition, also refers to adverse events or suspected adverse reactions that are mentioned in the investigator brochure as occurring with a class of drugs or as anticipated from the pharmacological properties of the drug, but are not specifically mentioned as occurring with the particular drug under investigation.

Serious

An adverse event or suspected adverse reaction is considered "serious" if, in the view of either the investigator or sponsor (UNIVERSITY OF MICHIGAN), it results in any of the following outcomes:

- Death
- A life-threatening adverse event
- Inpatient hospitalization or prolongation of existing hospitalization
- A persistent or significant incapacity or substantial disruption of the ability to conduct normal life functions
- A congenital anomaly/birth defect.
- Important medical events that may not result in death, be life-threatening, or require hospitalization may be considered serious when, based upon appropriate medical judgment, they may jeopardize the patient or subject and may require medical or surgical intervention to prevent one of the outcomes listed in this definition. Examples of such medical events include allergic bronchospasm requiring intensive treatment in an emergency room or at home, blood dyscrasias or convulsions that do not result in inpatient hospitalization, or the development of drug dependency or drug abuse.

Previously planned (prior to signing the informed consent form) surgeries should not be reported as SAEs unless the underlying medical condition has worsened during the course of the study. Preplanned hospitalizations or procedures for preexisting conditions that are already recorded in the patient's medical history at the time of study enrollment should not be considered SAEs. Hospitalization or prolongation of hospitalization without a precipitating clinical AE (for example, for the administration of study therapy or other protocol-required procedure) should not be considered SAEs. However, if the preexisting condition worsened during the course of the study, it should be reported as an SAE.

Life-threatening

An adverse event or suspected adverse reaction is considered "life-threatening" if, in the view of either the investigator or sponsor, its occurrence places the patient or subject at immediate risk of death. It does not include an adverse event

or suspected adverse reaction that, had it occurred in a more severe form, might have caused death.

- 12.1.3 The following adverse events are excluded from SAE reporting:
 - 12.1.3.1 All moderate events (grade 2) or hematologic serious events (grade 3) due to the patient's cancer or the treatment which are common toxicities and expected, including but not limited to alopecia, fatigue, lymphopenia, headache, nausea, vomiting, and anorexia. These will be noted in the patient's medical records. Events which are unexpected and possibly, probably or definitely related will be reported in 15 days (grade 2) or 7 days (grade 3).)
 - 12.1.3.2 Hospitalization secondary to expected cancer morbidity:
 - 12.1.3.3 Admission for palliative care or pain management
 - 12.1.3.4 Planned hospitalizations for surgical procedures either related or unrelated to the patient's cancer.
 - 12.1.3.5 Emergency Department visits not related to study treatment including accidental injury.

12.1.4 Adverse Event Characteristics

CTCAE terminology

Adverse events (AE's) will use the descriptions and grading scales found in the revised National Cancer Institute (NCI) Common Toxicity Criteria (CTC), version 4.03.

Attribution of the AE:

The investigator is responsible for assignment of attribution.

Definite – The AE is clearly related to the investigational agent/intervention.

Probable – The AE is likely related to the investigational agent/intervention.

Possible – The AE may be related to the investigational agent/intervention.

Unlikely – The AE is doubtfully related to the investigational agent/intervention.

Unrelated – The AE is clearly NOT related to the investigational agent/intervention.

12.2 Data Safety and Monitoring

This trial will be monitored in accordance with the NCI approved University of Michigan Comprehensive Cancer Center Data and Safety Monitoring Plan.

The study specific Data and Safety Monitoring Committee (DSMC), consisting of the protocol investigators, data manager or designee, and other members of the study team involved with the conduct of the trial, will meet quarterly or more frequently depending on the activity of the protocol. The discussion will include matters related to the safety of study participants (SAE/UaP reporting), validity and integrity of the data, enrollment rate relative to expectations, characteristics of participants, retention of participants, adherence to the protocol (potential or real protocol deviations) and data completeness.

At the regular DSMC meetings, the protocol specific Data and Safety Monitoring Report form will be completed. The report will be signed by the Principal Investigator or by one of the co-investigators.

Data and Safety Monitoring Reports will be submitted to the University of Michigan Comprehensive Cancer Center Data and Safety Monitoring Board (DSMB) on a quarterly basis for independent review.

References:

- 1. M. R. Gilbert, M. Wang, K Aldape et al. RTOG 0525: A randomized phase III trial comparing standard adjuvant temozolomide (TMZ) with a dose-dense schedule in newly diagnosed glioblastoma (GBM), J Clin Oncol 29: #2006, 2011
- 3. Stupp, R., M. Hegi, et al. Effects of RT with concomitant and adjuvant temozolomide versus RT alone on survival in glioblastoma in a randomised phase III study: 5-year analysis of the EORTC-NCIC trial. Lancet oncology 10(5): 459-66, 2009.
- 4. Stupp, R., W.P. Mason, M.J. van den Bent, et al., Radiotherapy plus concomitant and adjuvant temozolomide for glioblastoma. N Engl J Med, 352(10): 987-96, 2005
- 6. M. Tanaka, Y. Ino and K. Nakagawa, *et al.* High-dose conformal radiotherapy for supratentorial malignant glioma: A historical comparison. *Lancet Oncol*, 6:953–960,2005

Appendix 1:

100	Normal; no complaints; no evidence of disease
90	Able to carry on normal activity; minor signs or symptoms of disease
80	Normal activity with effort; some sign or symptoms of disease
70	Cares for self; unable to carry on normal activity of do active work
60	Requires occasional assistance, but is able to care for most personal needs
50	Requires considerable assistance and frequent medical care
40	Disabled; requires special care and assistance
30	Severely disabled; hospitalization is indicated, although death not imminent
20	Very sick; hospitalization necessary; active support treatment is necessary
10	Moribund; fatal processes progressing rapidly
0	Dead

